4.3.1 Screening

Pre-enrollment screening will be performed for patients who are consented for screening and willing to provide pre-trial tumor material for Rb1 testing. Sites are required to make a reservation using the CTSU OPEN Slot Reservation System before they ship the samples to UCSF for screening. Screening is facilitated by having pre-enrollment screening questions completed by a site registrar in the Prerequisite screen of OPEN. The site must complete the steps up to 'Prerequisite' to obtain the Enrollment tracking number which will be used for labeling the slides. OPEN enrollment will not proceed from the Prerequisite screen until the UCSF BTRC lab receives the tumor material, analyzes the tissue and captures the Rb1 result into the PBTC ProtoLab database.

Completing the Prerequisite screen sends an automatic email to the UCSF BTRC lab and site registrar with information on the screening process. Once the Rb1 result is entered in ProtoLab by UCSF BTRC lab, an automatic email will be sent to the site registrar and the responsible PBTC Protocol Coordinator indicating that enrollment may proceed. Based on the communicated Rb1 screening result, the site registrar must return to OPEN and complete the process – either completes enrollment of a patient for treatment who passes the screening, or removes the reservation of the patient who fails the screening.

Sites will be notified of the results of the Rb1 testing within 2 weeks. All screened patients who are eligible for participating in the PBTC-042 study must be enrolled via OPEN within 10 days of the site notification of a patient's Rb1 status.

Further instructional information is provided on the OPEN tab of the CTSU members' side of the CTSU website at <https://www.ctsu.org> or at <https://open.ctsu.org>. For any additional questions contact the CTSU Help Desk at [name] or [contact].

5 TREATMENT PLAN

Treatment will be administered on an outpatient basis. Reported adverse events and potential risks are described in Section 7. Appropriate dose modifications are described in Section 6.2. No investigational or commercial agents or therapies other than those described below may be administered with the intent to treat the patient's tumor. Treatment must be initiated within seven (7) days of enrollment.

5.1 Agent Administration

PD-0332991 (IBRANCE) is currently available as 75, 100, and 125 mg capsules (No liquid formulation is currently available). PD-0332991 (IBRANCE) will be given oral daily for 21 days followed by a week rest (one course = 28 days) for 24 months (26 courses). The starting dose will be 50 mg/m²/day for stratum I. The starting dose for stratum II will be one dose level below the MTD for stratum I (50 mg/m²/day).

Dosing is based on BSA calculated at the beginning of each course of therapy. The dose prescribed should be rounded to the nearest deliverable dose based on the BSA adjustment and the available capsule sizes. Dosing Tables are available in [Appendix D](#). Patients will be provided with a Medication Diary for PD-0332991 (IBRANCE), instructed in its use, and asked to bring the diary as well as the remaining capsule bottles with them to each appointment. The Patient Diary is available on the PBTC-042 webpage.

PD-0332991 (IBRANCE) should be taken with food. Patients are encouraged to take their dose at approximately the same time each day. Capsules should be swallowed whole (do not chew, crush or open them prior to swallowing). Capsules should not be ingested if they are broken, cracked, or otherwise not intact. Patients should be advised to drink plenty of water or take hydration fluids to avoid dehydration if diarrhea occurs. Patients who vomit a dose of PD-0332991 (IBRANCE) can be re-dosed if capsule is intact in the vomitus, and appropriate anti-emetic therapy should be implemented prior to the next scheduled dose (see [Appendix B](#) for contraindicated anti-emetic medications).

5.1.1 Dose-finding Period

The dose finding period begins with the initial dose of PD-0332991 (IBRANCE) and ends on the last day of course 1. Should there be a delay starting the subsequent course, dose finding will complete on the start date of the subsequent course.

Dose escalations will be based on toxicities observed during the dose finding period.

5.1.2 Dose Escalation Schedule

The pediatric equivalent of the adult MTD for the once daily administration of PD-0332991 (IBRANCE) based on a 3-week on/1 week off schedule is approximately 75mg/m². PD-0332991 (IBRANCE) dosing will begin at 50 mg/m². The PD-0332991 (IBRANCE) dose will be increased in subsequent cohorts until the MTD is reached ([Table 7](#)) or the highest proposed dose is determined to be safe.

The

[Table 7](#) below lists the proposed dose levels to be studied along with the BSA restrictions for each dose level for both Strata I and II. At the time of submission of version 8.0, a total of 21 patients had been enrolled in stratum I. No DLTs were observed in 3 patients enrolled in dose

level 1 and 6 patients enrolled in dose level 2. At dose level 3, a total of 6 patients were enrolled and 2 were inevaluable for toxicity assessment. Two of 4 evaluable patients at this dose level experienced DLTs (grade 4 neutropenia); hence the MTD was exceeded at dose level 3. The MTD for stratum I was determined as dose level 2 (75 mg/m²/day) and this stratum has been closed to accrual.

The starting dose level for stratum II is one dose level below the stratum I MTD (i.e. 50 mg/m²/day). If this dose is well tolerated in the initial cohort of patients enrolled on Stratum II, the dose will be escalated to 75 mg/m²/day for the next cohort of patients. No further escalation will be allowed in this stratum.

[figure not shown]
The plot below the table demonstrates that dosing using the available capsule sizes is feasible for the proposed dose levels using the BSA restrictions outlined in the table below. It is not however possible to include a level below 50mg/m²/day due to the capsule size limitations. No intra-patient dose escalation will be permitted on the protocol. Only DLTs observed during the dose-finding period will be used to guide dose escalation. Dose escalation will be governed by the Rolling-6 statistical design separately in each of the two strata, as described in section [13.2](#) of the protocol.

Table 7
Stratum I and II: PD-0332991 (IBRANCE) Dosing Regimen and BSA Restrictions

Dose Level	Dose (mg/m ²)	BSA (m ²)
1*	50	≥ 1.20
2**	75	≥ 0.93
3	95	≥ 0.70

* Starting dose for Stratum II

** MTD for stratum I

5.2 Dose Limiting Toxicity

Toxicities will be graded according to CTCAE version 4.0 of the NCI Common Terminology Criteria for Adverse Events CTCAE version 4.0 is identified and located on the CTEP website at http://ctep.cancer.gov/protocolDevelopment/electronic_applications/ctc.htm.

All appropriate treatment areas should have access to a copy of CTCAE version 4.0. Management and dose modifications associated with adverse events are outlined in Section 6.

DLT will be defined as any of the events listed in this section that are at least possibly related to the investigational agent that occur during the dose-finding period regardless of expectedness. Management and dose modifications for toxicities which occur outside of the dose-finding period should also follow section 6; however these will not be considered dose limiting for the purpose of dose escalation.

Patients who come off therapy for reasons other than toxicity before completing the dose-finding period may be replaced for purposes of estimating the MTD, as discussed in section 13.1.

5.2.1 The following are Dose-Limiting Toxicities (DLT's)

- A PD-0332991 (IBRANCE) related adverse event will be considered dose-limiting if it leads to a dose reduction or permanent cessation of treatment during the first course of therapy. All dose modifications in all courses are to follow the guidelines provided in section 6.2.

- Inability to receive the next cycle of PD-0332991 (IBRANCE) within two weeks of the last dose because of lack of hematologic recovery or persisting non-hematologic toxicity.

5.2.1.1 Non-hematologic dose limiting toxicity is defined as:

- Any grade 4 non-hematologic toxicity
- Any grade 3 non-hematologic toxicity with the exception of:
 - Grade 3 nausea and vomiting of < 5 days
 - Grade 3 diarrhea and/or electrolyte disturbances which have not been maximally treated
 - Grade 3 AST/ALT elevation that returns to levels meeting eligibility criteria within 7 days of study drug interruption and does not recur upon restarting drug.
- Any Grade 2 non-hematologic toxicity that persists for > 7 days and is considered medically significant or sufficiently intolerable by patients requires treatment interruption.

5.2.1.2 Hematologic dose limiting toxicity is defined as:

- Grade 3 neutropenia with fever and sepsis
- Any Grade 4 hematologic toxicity with the exception of lymphopenia
- Grade 3 thrombocytopenia and/or requiring a platelet transfusion on 2 separate days within a 7-day period

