2.2.3 Adult Clinical Trials

2.2.3.1 Phase I trial of PD-0332991 in adults with recurrent solid tumors
PD-0332991 has been tested in a Phase I trial in adults with recurrent solid tumors and lymphomas (A5481001) that explored two different schedules of the drug. In the first schedule reported by Schwartz et al., adult patients with Rb1 positive recurrent solid tumors were enrolled

across four cohorts using doses of 100 mg, 150 mg, 200, and 225 mg given orally daily for 14 days every 3 weeks (Schedule 2/1).³ No DLTs were observed at the 100 mg or 150 mg dose level. Dose limiting myelosuppression occurred in 2/3 patients at the 225 mg dose level [Grade IV neutropenia and thrombocytopenia (n=1) and Grade III neutropenia with delayed recovery (n=1)]. An intermediate dose of 200 mg/day was chosen. After only one DLT was observed (Grade III neutropenia and thrombocytopenia) in 6 enrolled patients at this dose, the cohort was expanded to a total of 20 patients. Three additional patients suffered DLT (Grade III myelosuppression with delayed recovery) with an overall 20% rate of DLT at this dose level. Since this did not exceed the preset limit of 33%, 200 mg/day for 14 days every 4 weeks was declared the MTD. Additional toxicities were mild and included Grade I fatigue and Grade I-II diarrhea. No patient had Grade 3 prolongation of QTc interval on EKG during therapy. Plasma PK studies revealed a dose proportional increase in C_{max} and AUC_{0-10} on days 1 and 8. In samples obtained from patients receiving 200 mg q daily, repeated dosing led to steady state levels. The median T_{max} was 4.2 hours and volume of distribution was 3241 liters (more than the adult total body water of 42 liters) suggesting extensive tissue penetration. PD-0332991 was eliminated slowly with a mean $T_{1/2}$ of 26.7 hours.²¹ One patient with a non-seminomatous germ cell tumor of the testis achieved a prolonged partial response and 9 had SD. Six patients with SD had treatment for ≥ 4 cycles and 2 for ≥ 10 cycles.

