5.3 Criteria for starting subsequent courses

A course may be repeated every 28 days if the patient has at least stable disease and has again met laboratory parameters as defined in Section [3.2.10](#). The labs can be performed within 48 hours prior to the start of each course. If a patient does not meet these parameters at the end of the treatment course (at day 28), then PD-0332991 (IBRANCE) can be held for up to 7 days until parameters meet the eligibility criteria. Drug can be held for up to 14 days in patients who undergo surgical procedures for reasons other than tumor progression to allow for proper wound healing.

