5.5.3 Data Submission Schedule for Patients Off Treatment

Subjects will be monitored for the resolution (or return to baseline) of all toxicities considered at least possible related to PD-0332991 (IBRANCE) occurring while on treatment and/or within 30 days after the last administration of study drug. Toxicities that are ongoing at the end of day 30 of last treatment date will be followed until resolution or return to baseline or until the patient is

off study.

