13 STATISTICAL CONSIDERATIONS

13.1 Evaluability

13.1.1 Evaluability for DLT Assessment

Patients who receive at least one dose of the study drug and are taken off treatment for toxicity during the first course (dose-finding period) are evaluable for estimating the MTD. Similarly patients who have to go off treatment due to inability to de-escalate following toxicity because of BSA restrictions are also evaluable for DLT assessment and for estimating the MTD.

Patients who receive approximately 85% (17 or more doses) of prescribed therapy during the dose-finding period but who progress prior to completing the course may be considered evaluable for estimating the MTD, as long as no additional anti-cancer therapy or supportive care that would confound the interpretation of any observed toxicity or side effect is given. Patients must have completed all of the clinical and laboratory monitoring requirements specified by the protocol up to the time of disease progression for them to be considered evaluable for MTD.

Patients who have completed all therapy during the dose-finding period but who failed to comply with all the specified clinical and laboratory monitoring requirements for the first course will be considered inevaluable for estimating the MTD and replaced.

Patients who receive less than 17 doses of the protocol specified therapy and who go off treatment for reasons other than toxicity (e.g. progressive disease, withdrawal of consent etc.) during the dose finding period will be considered inevaluable for estimating the MTD and will be replaced. However as noted above, patients who go off treatment due to inability to de-escalate following toxicity as a result of BSA restrictions are evaluable.

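### The delayed-recovery DLT can be scored only in patients otherwise due to start course 2, so a patient with unresolved toxicity who leaves at the end of course 1 for another reason can be counted as DLT-free

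*Combined protocol and SAP*

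**What the plan says.** **The criterion.** Section 5.2.1 includes among the DLTs the "Inability to receive the next cycle of PD-0332991 (IBRANCE) within two weeks of the last dose because of lack of hematologic recovery"; the same bullet has a second limb for persisting non-hematologic toxicity.

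**The window.** Under Section 5.1.1 the dose-finding period "ends on the last day of course 1". One extension is given: "Should there be a delay starting the subsequent course, dose finding will complete on the start date of the subsequent course". Sections 5.1.2 and 5.2 let only events within this period guide escalation.

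**Starting course 2.** Section 5.3 allows a further course "if the patient has at least stable disease and has again met laboratory parameters" set out in Section 3.2.10. If the parameters are not met at Day 28, drug "can be held for up to 7 days until parameters meet the eligibility criteria".

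**Evaluability.** Section 13.1.1 makes inevaluable, and replaces, patients described as "Patients who receive less than 17 doses of the protocol specified therapy and who go off treatment for reasons other than toxicity" during the dose-finding period. Patients who took all doses are inevaluable only if course 1 monitoring was not complied with. Patients who progress before completing the course after 17 or more doses may be evaluable, with monitoring required only up to progression. Section 5.2 says that patients who leave for non-toxicity reasons before completing the dose-finding period may be replaced.

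**Follow-up.** Section 5.5.3 states: "Subjects will be monitored for the resolution (or return to baseline) of all toxicities considered at least possible related" to study drug. It does not connect this follow-up to DLT scoring.

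**The concern.** The bullet turns on the reason course 2 was not given, not on whether the patient recovered. Progression bars course 2 under Section 5.3 whatever the counts, and withdrawal ends treatment whatever the counts. In either case the stated cause of not receiving the next cycle is not toxicity, so the bullet is not met even if the toxicity is still present.

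Such a patient, with all doses taken and course 1 monitoring complete, fits neither inevaluability rule in Section 13.1.1. The natural result is an evaluable patient without a DLT.

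At stake is the Rolling-6 count in Stratum II, which was still accruing at version 8.0 with four patients enrolled. The Schema expects more myelosuppression in these heavily pretreated patients. One reclassified patient is enough to change a decision under Section 13.2.

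**Working it through.** **1. Figures in the plan.** Stratum II maximum: 2 levels × 6 + 6 expansion = 18, as stated in Section 13.3. Evaluability threshold: the Day 2 dose is held (Section 9.2.2), so 20 doses are planned and 17/20 = 85%, as stated in Section 13.1.1. The plan states no operating characteristic that depends on this DLT, so there is none to reproduce.

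**2. Timeline, with the last dose on Day 21.**
- Two-week limit in 5.2.1: 21 + 14 = Day 35.
- Hold allowed by 5.3: 28 + 7 = Day 35, which agrees.
- Default end of dose finding: Day 28.
- Observed after the last dose by a patient leaving on Day 28: 28 − 21 = 7 of 14 days.
- Extended end of dose finding: the course 2 start date, which never arrives if course 2 is not started.

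**3. Does another rule catch this patient?**
- *By grade (5.2.1.2):* Grade 4 hematologic toxicity other than lymphopenia, and Grade 3 neutropenia with fever and sepsis, are DLTs for everyone. Grade 3 thrombocytopenia is listed separately. The hematologic gap is therefore mainly lesser neutropenia that has not recovered.
- *First bullet of 5.2.1:* requires a dose reduction or permanent cessation caused by the event during course 1. Section 6.2 maintains the dose for non-dose-limiting Grade 3 hematologic events, so this need not be triggered.
- *Replacement (5.2):* available if the exit comes before dose finding is complete, for example during a hold, but discretionary.
- *Follow-up (5.5.3):* could supply the recovery data, but Section 5.5.4 takes a patient off study when another anti-cancer therapy starts.

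**4. Effect on a decision.** Under Section 13.2, 2 DLTs in 6 is too toxic and 1 in 6 passes. With three evaluable patients, 1 DLT means stay and 0 means escalate. One unscored DLT moves either case.

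**5. Size, on assumed inputs.** Let p be the true DLT rate, f the share of DLTs that appear only as delayed recovery, and q the share of those patients who leave for another reason and are scored DLT-free. Then

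- observed rate p′ = p(1 − f·q)
- P(at most 1 of 6) = (1 − p′)⁶ + 6p′(1 − p′)⁵

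The documents give neither p nor q. For f:
- Adult 2/1-schedule study (2.2.3.1): six DLTs. Four involved delayed recovery ("Three additional patients suffered DLT (Grade III myelosuppression with delayed recovery", plus one at 225 mg), so f = 4/6 = 0.67. Only one of the six is explicitly neutropenia with delayed recovery, giving f = 1/6 = 0.17.
- Adult 3/1-schedule cohort (2.2.3.1), the schedule used here: five DLTs of Grade III or IV neutropenia, with no mention of delayed recovery.
- Stratum I: both DLTs were Grade 4, so f = 0.

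At p = 0.33:

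| f | q | p′ | P(at most 1 of 6) |
|---|---|---|---|
| 0 | any | 0.330 | 35.8% |
| 0.17 | 10% | 0.324 | 36.9% |
| 0.67 | 5% | 0.319 | 38.0% |
| 0.67 | 10% | 0.308 | 40.3% |
| 0.67 | 20% | 0.286 | 45.1% |
| 0.67 | 30% | 0.264 | 50.2% |

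A wider grid (p from 25% to 50%, f from 25% to 50%, q from 10% to 30%) raises the chance of passing by 1.2 to 10.5 points. On a three-then-six path, with pass probability (1 − p′)³ + 3p′(1 − p′)²(1 − p′)³, the rise is 1.4 to 10.6 points.

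**The case against.** Four points on the other side have force.

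- **Starting course 2 is not required.** A reader might infer that the DLT can be scored only in patients who go on to course 2. That is not so: a patient kept off course 2 past Day 35 by low counts meets the bullet without ever starting it. The gap is confined to patients who miss course 2 for another reason.
- **Other routes exist.** A reader might also infer that this bullet is the only way prolonged Grade 3 neutropenia becomes a DLT. A decision to stop during course 1 because of the counts falls under the first bullet. Only exits unrelated to toxicity remain.
- **DLT-free scoring is not mandated in every case.** If low counts delay course 2, dose finding can be read as still open, and Section 5.2 then allows replacement. Evaluability after progression during course 1 is also discretionary. This stands for exits during a hold or before the course ends. It does not settle the patient who leaves at Day 28 with doses and monitoring complete, and leaving the choice open is itself a reason to fix the rule in advance.
- **Such exits may be few, and there are safeguards.** The first on-treatment MRI follows course 2, non-toxicity exits before 17 doses are already replaced, and the interval in question is about one week. Six more patients are treated once a dose is selected, with possible de-escalation. Stratum II is capped at the Stratum I MTD, and all treated patients enter the safety tables. These limit the consequence but do not say how the patient is scored in the dose-finding count.

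**Conclusion.** The concern holds in this limited form: the delayed-recovery DLT is scorable only in patients otherwise due to start course 2, and the present text can place a patient with unresolved drug-related toxicity in the Rolling-6 count as DLT-free after 7 of the 14 days. This follows from reading Sections 5.1.1, 5.2.1, 5.3 and 13.1.1 together and needs no assumed rate.

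The effect is probably small. At a true DLT rate of 33%, the chance of passing on at most 1 of 6 goes from 36% to about 37% at f = 0.17 and q = 10%. It reaches 50% only with f = 0.67 and q = 30%, and does not move at f = 0. A reader might take the upper figure as evidence of material bias. The documents do not support that: q is not reported, and f = 0.67 comes from adults on a different schedule and at different doses, whereas Stratum I gives f = 0.

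The change is still worth making, because the decision turns on single patients, Stratum II is still accruing, and the remedy is cheap.

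**What to change.** These changes concern scoring only; no dose or treatment rule is altered.

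1. **Section 5.2.1.** Keep both limbs of the bullet and the existing two-week limit. State that it is judged on non-recovery from drug-related toxicity at that limit, whether or not course 2 is planned. Tying it to Section 3.2.10 alone would not do, because that section lists laboratory parameters and the non-hematologic limb would lose its non-laboratory events.
2. **Section 5.1.1.** State that when course 2 is not started and drug-related toxicity is unresolved, the dose-finding period ends at recovery or at the existing two-week limit, whichever is first.
3. **Sections 13.1.1 and 5.2.** State that such a patient who is not observed to recovery or to the limit, including because another anti-cancer therapy starts (5.5.4), is inevaluable and replaced, not counted as DLT-free. Align the discretionary replacement wording in 5.2 with this.

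The follow-up in Section 5.5.3 can supply the data while the patient remains on study. The cost is a few sentences in an amendment and an occasional extra replacement patient, most likely among those who progress and move quickly to other therapy. The maximum of 18 evaluable patients in Stratum II does not change.

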5.5.2 Off Treatment Criteria

At the discontinuation of treatment, the “Off Treatment Date” is to be recorded in the eCRF and is to be consistent with the reason given for going off treatment. The “Last Treatment Date” is defined as the last date that the patient received protocol based therapy. Date of “off treatment” must be the greatest of the date of last treatment, date of procedure, date of patient assessment, notification of patient/family decision, or decision made by the physician that resulted in the patient being taken off protocol treatment. The reason for discontinuation of treatment must be documented by the attending investigator in the medical record and recorded in the eCRF.

Patients will be considered Off Treatment for the following reasons:

- Development of unacceptable toxicity as outlined in section [5.2.1](#). See section [7](#) for specific reporting requirements.
- Progressive disease (PD) as described in section [11.1.4](#).
- Development of a medical or psychiatric illness that in the investigator's judgment renders the patient incapable of further therapy on this protocol or the treating physician determines continuation on this study is not in the patient's best interest.
- Interruption greater than 14 days of continued drug administration for reasons unrelated to toxicity
- The patient, parent or legal guardian refuses further treatment on this protocol.
- Completion of all protocol defined treatment
- Pregnancy
- Non Compliance that in the opinion of the investigator does not allow for ongoing participation.
- Termination of the study by the sponsor
- Investigational Agent/Device manufacturer can no longer provide the study agent.

Patients who are off protocol therapy must be followed until an Off Study Criterion is met.

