6.2 Hematologic and Non-Hematologic Adverse Events and Management

Table 8

Event	AE Grade or Observation	Dose Modification
Diarrhea or other non-hematologic toxicity	Grade 1 or 2	Maintain dose; continue anti-diarrheal treatment.
	Grade 3 (non-dose limiting)	Hold PD-0332991 (IBRANCE) and maximally treat. If toxicity resolves to meet on study parameters within 14 days of drug discontinuation or (as outlined in Section 5.2.1.1), restart treatment at the same dose.
	Grade 3 or 4 (dose limiting)	Hold PD-0332991 (IBRANCE) and maximally treat. If toxicity resolves to meet on study parameters with 14 days of drug discontinuation, restart treatment at next lower dose level if patient at dose level 2 or 3 and meets BSA requirements for the next lower dose level. If patient at dose level 1 or with BSAs smaller than what is required should come off treatment permanently. If toxicity does not resolve to meet study eligibility parameters within 14 days of drug discontinuation, the patient must be removed from protocol therapy. If dose limiting toxicity recurs in a patient who has resumed treatment at the reduced dose level, the patient must be removed from protocol therapy.
Hematologic	Grade 1 or 2	Maintain dose.
	Grade 3 (non-dose limiting)	Maintain dose.
	Grade 3 or 4 (dose limiting)	Hold PD-0332991 (IBRANCE). Counts should be checked at least twice weekly (3-4 days apart) during this time. If toxicity resolves to meet on study parameters with 14 days of drug discontinuation, restart treatment at next lower dose level, if patient is at dose level 2 or 3 and meets BSA requirements for the next lower dose level. If patient at dose level 1 or with BSAs smaller than what is required should come off treatment permanently. If toxicity does not resolve to meet study eligibility parameters within 14 days of drug discontinuation, the patient must be removed from protocol therapy. If dose limiting toxicity recurs in a patient who has resumed treatment at the reduced dose level, the patient must be removed from protocol therapy.

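### Table 8 says to maintain dose for every Grade 1–2 non-hematologic event, yet section 5.2.1.1 counts one kind of persistent Grade 2 event as dose limiting

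*Combined protocol and SAP*

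**What the plan says.** - **Scope of a DLT.** Section 5.2: "DLT will be defined as any of the events listed in this section that are at least possibly related to the investigational agent", provided the event falls in the dose-finding period, which is course 1.
- **The Grade 2 criterion.** Section 5.2.1.1, in the list that defines non-hematologic DLTs: "Any Grade 2 non-hematologic toxicity that persists for > 7 days and is considered medically significant or sufficiently intolerable by patients requires treatment interruption".
- **Who decides management.** Section 5.2 refers management and dose changes to section 6. Section 5.2.1 adds: "All dose modifications in all courses are to follow the guidelines provided in section 6.2".
- **Table 8, non-hematologic block.** It covers diarrhea and every other non-hematologic toxicity, in three rows. Grade 1 or 2: "Maintain dose; continue anti-diarrheal treatment". Grade 3, not dose limiting: hold, treat, and on resolution within 14 days "or (as outlined in Section 5.2.1.1), restart treatment at the same dose". Grade 3 or 4, dose limiting: hold and, on resolution within 14 days, restart one level lower if the patient is at level 2 or 3 and body surface area (BSA) allows; otherwise come off treatment.
- **Other routes to a DLT.** Under section 5.2.1 a drug-related event is also a DLT if "it leads to a dose reduction or permanent cessation of treatment during the first course of therapy". So is failure to start the next cycle within two weeks of the last dose "because of lack of hematologic recovery or persisting non-hematologic toxicity".

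**The concern.** The same event meets two rules. Section 5.2.1.1 treats a lasting, significant or intolerable Grade 2 event as dose limiting and links it to stopping drug. The only Table 8 row that fits a Grade 2 event says to carry on. Table 8 has no hold, resolution window, restart dose or removal rule for it.

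The first thing at stake is patient management: a child could stay on full dose through a DLT, on the written instruction of the section that governs dose changes, while stratum II is still enrolling. The second is conditional: if an actual interruption is part of the DLT definition, a site that obeys Table 8 does not interrupt, and the event might then not qualify as a DLT.

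**Working it through.** The plan states no figure on this point, so most of the check is textual. One calculation bounds the exposure.

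**1. Does Table 8 leave room for a hold at Grade 2?** Table 8 says hold where it means hold. Its Grade 3 non-dose-limiting row holds drug and then resumes at the same dose, so the table separates interrupting from keeping the dose level. Read plainly, the Grade 1–2 row means no interruption. The table was also written with the DLT list in view: it cites 5.2.1.1 and splits Grade 3 by dose-limiting status. Grade 2 is not split.

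**2. What does the Grade 2 sentence require?** It is ungrammatical and has three readings.

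| Reading of the interruption clause | Conflict with Table 8 |
|---|---|
| Condition on both the significant and the intolerable branch | Both kinds of event go with interruption; Table 8 says continue |
| Condition on the intolerable branch only | Direct conflict for intolerable events; a significant event is a DLT that Table 8 does not hold for |
| Instruction to interrupt | Opposite instructions |

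On every reading, at least the intolerable event goes with interruption. On the first two it also matters whether the clause means that interruption was needed or that it took place. If it must have taken place, following Table 8 keeps the criterion from being met.

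**3. How many course-1 doses can be affected?** Inputs: 21 dosing days (section 5.1) and the day 2 dose held for pharmacokinetics (section 9.2.2).
- Course-1 doses: 21 − 1 = 20. This agrees with section 13.1.1, where 17 doses is about 85%: 17/20 = 0.85.
- With onset on day d, more than 7 days have passed on day d + 8. Doses from then to day 21: 21 − (d + 8) + 1 = 14 − d, and zero from d = 14. The held day 2 always falls before this window.
- Onset day 1: 13 doses. Day 4: 10. Day 7: 7. Day 10: 4. Day 13: 1. Day 14 or later: 0.
- If the onset day is counted, the window starts on day d + 7 and the number is 15 − d: at most 14, and zero from day 15.

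This bound is for course 1. Section 5.2 applies section 6 to later courses too, but events there do not count for escalation.

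**4. Do other provisions close the gap?** In part.
- The next-cycle criterion in 5.2.1 catches a toxicity that blocks course 2. Section 5.3, however, restarts on disease status and laboratory values, so a Grade 2 symptom with no laboratory correlate need not block it.
- Section 5.5.2 lets the treating physician stop treatment, and a permanent stop in course 1 for a drug-related event is a DLT.
- Neither tells a site to hold drug during the course.

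**5. How often would it arise?** The documents give no rate of Grade 2 DLTs. Both stratum I DLTs were grade 4 neutropenia (section 5.1.2). The five adult DLTs in the 3/1-schedule dose-level results were Grade III or IV neutropenia, with other toxicities described as mild (section 2.2.3.1).

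**The case against.** The strongest reply is that the two sections have different jobs. Section 5.2.1.1 is a counting definition, section 6 is the management rule, and section 5.2 says so. On that view Table 8 has an omission and there are no opposing orders. A site assessing DLTs in course 1 must read 5.2 anyway, and the physician can always stop.

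Part of this stands. DLT status is set by 5.2 and not by Table 8, so a site that reads both sections can recognize and report the event. But Table 8 is not silent on Grade 2: it covers every Grade 2 non-hematologic event and says to maintain dose. The division of roles makes that row the operative instruction, and nothing in the protocol makes an exception to it.

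A reader might also infer a second conflict. Section 5.5.2 takes patients off treatment for "Development of unacceptable toxicity as outlined in section" 5.2.1, which is the DLT list, while Table 8 allows some patients with a DLT to restart one level lower. The documents do not support this as a real contradiction. Section 5.2.1 itself counts a dose reduction as a DLT, so it foresees a patient who continues at a lower dose, and it sends dose changes to section 6.2. Section 13.1.1 treats inability to de-escalate as a special case. What remains is a loose cross-reference that changes neither the DLT count nor evaluability.

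**Conclusion.** The inconsistency is real and minor. Followed as written, Table 8 keeps a child on full dose through a Grade 2 event that 5.2.1.1 counts as dose limiting, over at most 13 of 20 course-1 doses (14 if the onset day counts). That maximum needs onset on day 1. The frequency is unknown and may be zero.

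A reader might infer that DLTs have been under-counted or that a dose decision is biased. The documents do not support that. An event would be lost only if a site followed Table 8 and either did not report it or took actual interruption to be part of the definition, and there is no record of this. The stratum I maximum tolerated dose is unaffected: level 3 was exceeded on two grade 4 neutropenias, and section 5.1.2 reports no DLT among six patients at level 2.

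The conclusion rests on reading the maintain-dose row as no interruption, which Table 8's own use of hold supports.

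**What to change.** 1. Limit Table 8's Grade 1–2 non-hematologic row to events that are not dose limiting under 5.2.1.1.
2. Either extend the dose-limiting row to Grade 2 events that meet 5.2.1.1, or add a separate row for them. It should say to hold drug, use the same 14-day resolution window and state the restart rule. The rule must cover level 1, where stratum II is enrolling and no lower level exists: say whether such a patient restarts at the same dose or comes off treatment. Simply extending the existing row would mean coming off.
3. Reword the Grade 2 sentence so that it turns on the need for interruption and not on whether the site actually interrupted, and so that it is clear which branch the clause covers. For example: a Grade 2 non-hematologic event lasting more than 7 days that is medically significant, or tolerated badly enough, to call for a hold, whether or not drug was held.
4. Before the next stratum II dose decision, check recorded course-1 drug-related Grade 2 events lasting more than 7 days against this definition.
5. Optional tidy-up: have 5.5.2 cite the removal conditions in 6.2 as well as 5.2.1.

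The cost is a short amendment: one limiting phrase, one table entry and one sentence. Section 6.1 already requires the study chair or co-chair to be told before any dosage modification. The check covers the 4 stratum II patients enrolled as of version 8.0 plus any since. Section 7 has drug-related Grade 2 events recorded, but the documents do not show that intolerability or the need to interrupt is captured, so a few site queries may be needed.
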